Outcome Assessor, To be hired. The Outcome Assessor will administer Part 2 of the Baseline assessment and follow-up assessments at 6 and 12 months in participants' homes masked to treatment assignment. The Outcome Assessor will obtain informed consent and administer Part 1 of the Baseline Assessment to participants who do not want to be consented in the hospital. [name] will supervise the Outcome Assessor.

Study Coordinator, [name]. [name] will be responsible for providing assistance to [name] with the overall conduct of the PREVENT trial. In addition, she will assist [name] in managing study data. Specifically, she will: 1) maintain administrative data bases (e.g., participant contact information); (2) manage the payment of participant incentives; and (3) send biweekly reports to the Outcome Assessor and CHW Interventionists to inform them of participants who are due for follow-up assessments and intervention visits. Drs. [name] and [name] will supervise the Research Coordinator.

Research Assistant, To be hired. The Research Assistant will be supported by the Department of Neurology at Jefferson. This person will be responsible for: (1) reviewing participants' medical charts at 6 and 12 months to collect data on current medications, diabetes quality metrics, and recent hospitalizations and ED visits; and (2) listen to audiotapes of data collection visits for quality assurance purposes.

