Health Literacy: To assess health literacy, we will use the Literacy Assessment for Diabetes (LAD). The LAD tests pronunciation of DM-related terms, and correlates highly with other literacy tests. Literacy will be considered as a potential covariate and treatment modifier.

Alcohol Use: Alcohol use will be assessed at baseline with the 3-item short form of the Alcohol Use Disorders Identification Test (AUDIT). The AUDIT has adequate sensitivity and specificity to identify potential alcohol abuse. Alcohol will be evaluated as a potential covariate.

DM-Specific Health Beliefs Model Scale: We will use this instrument as an exploratory outcome to assess change in DM-specific health beliefs [i.e., perceived benefits, side effects and general barriers to DM care (e.g., "I worry about the long term effects of my DM medication")], perceived susceptibility to DM complications, and perceived severity of DM.

Insurance Status and Type: We will classify insurance type as: government (Medicare, Medicaid, other government), private (Blue Cross/Blue Shield, other commercial, managed care), self-pay, other (industrial and worker's compensation, unclassified), unknown insurance, and no insurance. Insurance status/type will be a potential covariate.

Incident ED Visits and/or Hospitalizations: The primary efficacy analysis will consider the number of incident DM-related ED visits and/or hospitalizations (i.e., an "event") over 12 months. Each ED visit or hospitalization is counted as a single event (although an ED visit that leads to a hospitalization is counted once). A subsidiary outcome analysis will consider "all cause" events. To determine whether an "event" is DM-related or not, Co-l's [name] and [name] (masked to treatment assignment) will independently review the medical records of all "events," and make the determination. For descriptive purposes, we will also classify incident ED visits as "early" (i.e., ≤ 30 days post-baseline) vs. "late" (i.e., > 30 days). The ED physicians will be asked to rate whether each event is "related" (i.e., due to a similar or associated problem) vs. "not related", and "expected" (e.g., suture removal) vs. "unexpected" (i.e., a new medical problem). For discrepant determinations on whether the event is diabetes-related, co-investigator [name] will render a third determination, and the final classification will be based on the majority rating. When there is not a majority determination among

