8.2. Preservation of masking

This is a single-masked trial. The Outcome Assessor will be masked to treatment assignment. The PI, participants, the Project Director, the Study Coordinator, the CHW interventionists, the diabetes nurse educator, and PCPs treating participants randomized to PREVENT will be unmasked. Since this study is testing a behavioral intervention and there are no anticipated risks associated with study participation, there are no circumstances in which there will be unmasking based on untoward medical events.

An unavoidable aspect of behavioral intervention research is that participants are aware of their treatment assignments. Several measures will be undertaken to preserve the integrity of masking. First, the Outcome Assessor, who assesses all outcomes, will have no knowledge regarding treatment assignment. Masked staff will not have access to any data files or charts that contain information on treatment assignment. Hard copies of data will be stored in a locked, secure file room at Jefferson. Electronic copies will be stored on an encrypted, password protected server. Second. prior to performing any assessment, the Outcome Assessor will emphasize to all participants the importance of not revealing their treatment assignment. They will be instructed to call the Study Coordinator should they have any questions about this. Third, the Outcome Assessor and the CHW interventionists will be instructed to never discuss any of the participants with each other, either generally or specifically. Fourth, for quality control purposes, after each follow up assessment, the Outcome Assessor will be asked to indicate his/her best guess of which study group the participant is in, as well as his/her reasons for this estimate. If at any time the Outcome Assessor learns of a participant's treatment group, he/she will notify the Study Coordinator immediately, and she will document it so that statistical analyses can be adjusted accordingly. The biostatistician will specifically examine whether unmasking leads to the introduction of treatment-related biases in all reporting of study results. In addition, a research assistant who works in the PI's lab and is employed by the Department of Neurology at Jefferson, will be trained to conduct the follow-up assessments. If a participant's treatment assignment is revealed to the Outcome Assessor, the research assistant will conduct that particular participant's subsequent follow-up assessments.

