9.1. PREVENT

PREVENT is a collaborative intervention of PCPs, a DM nurse educator, and CHWs that aims to reduce the need for DM-related ED visits in AAs with DM. To achieve this goal, PREVENT uses culturally tailored strategies to improve DM self-care and access to care. Within 2 weeks of discharge from the ED or hospital, a CHW will begin to deliver six 90-minute in-home treatment sessions (during the 1st four months) and three booster sessions (over the next 8 months). The CHW will: 1) deliver culturally relevant DM self-care education: 2) use DM-specific Behavioral Activation to reinforce DM self-care skills, and 3) facilitate a telehealth visit with the participant's PCP (session 2), and three telehealth visits (sessions 3 and 5, and the 8-month booster session) with a DM nurse educator (Co-I [name], DNP, CDE). At every treatment session, the CHW will complete the Community Health Worker (CHW) Encounter Form. This brief standardized form characterizes CHW treatment activities and participant DM self-care practices. The CHW will upload the Form to the EMR (Epic) for the PCP's review after sessions 1 and 6 (at 4 months). This will enable the PCP to better engage the participant during the telehealth visit (session 2) and in subsequent office visits. For participants who do not have a Jefferson PCP, the CHW will fax the form to the PCP. [name] will supervise the CHW during twice monthly meetings. The CHW will make no treatment recommendations unless previously discussed with [name].

- Session 1: The CHW will establish rapport and describe the collaboration with the PCP and DM nurse educator. She will discuss the reasons for the participant's recent ED visit, experiences with DM self-care (e.g., adherence to medications, diet, glucose monitoring), and barriers (e.g., unhealthy family diet). The CHW will then review culturally relevant educational materials to build DM knowledge and skills according to national standards. The CHW will also rehearse and record a participant's questions (e.g., "Do I skip medications when traveling?") and health beliefs (e.g., "Sometimes I think prescription medications are addictive") to build confidence to discuss these issues with the PCP. The CHW will contact the JeffConnect scheduling office to schedule the PCP telehealth visit (session 2). The CHW will also refer participants (as needed) to social services to ensure that basic needs are met (e.g., safe housing, financial counseling, food security).

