12.4. Procedures for Data Checking and Editing

After completing an in-home assessment, the Outcome Assessor should not leave the participant's home until they check REDCap to verify that: (1) that the correct participant ID was selected; (2) all questionnaires are completed; and (3) missing data are properly coded. Once the Outcome Assessor gets back to the office, she will enter in REDCap all data that were collected on paper forms (e.g., LAD, MOCA). The Outcome Assessor should also check to be sure that all hard copies are properly labeled with the date of the assessment, the participant's initials and ID, and the assessment type (e.g., 6 months). Assessments should be marked as "unverified". The assessor will then email the Project Director and the Study Coordinator to inform them that the assessment was completed. The subject line of the email should contain the participant's initials and ID (for example, CRJC0001). The body of the email should contain the following completed table (note example provided). The image of the A1c readout should be attached to the email. The email must be sent the same day that the assessment occurred.

Notification of Completed Assessment Table

Participant ID:	CRJC00001
Assessment date:	9/14/18
Assessment:	Part 2 Baseline
Comments:	

Once the email has been sent, the Outcome Assessor should upload the recording of the assessment to the designated location on the shared drive. All tapes must be uploaded and all hard copies of paperwork must be turned into the Study Coordinator within 1 business day of the assessment. Staff will scan all hard copies and store them on the appropriate location of the shared drive. Staff will download the A1c image and store it in the appropriate location on the shared drive.

The Research Assistant, who is employed by the Department of Neurology at Jefferson and is not paid by this grant, will then review the tape and update the REDCap files as necessary. All data edits made by the Research Assistant must be recorded on the Assessment Check excel file, which will be stored on the shared drive. If additional information is required from the Outcome Assessor (for example, a skipped question), the Research Assistant will email the Outcome Assessor, the Project Director, and the Study Coordinator. The subject line should be the participant's initials and ID. The body of the email should include the following table:

Data Query Table

Participant ID:	CRJC00001
Assessment date:	9/14/18

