APPENDIX 6: PROCEDURES FOR RECORDING INCIDENT ED VISITS/HOSPITALIZATIONS

- 1) Whenever any staff learn of a new ED visit or hospitalization, they must complete an Incident Hospitalization/ED Visit Form. If the event was learned of at an assessment visit (baseline or FU), the Outcome Assessor will complete the required fields on the assessment in REDCap AND will complete an Incident Hospitalization/ED Visit Form in hard copy (not REDCap).
- 2) The completed Incident Hospitalization/ED Visit Form must be emailed to [name], [name], and [name] as soon as possible.
- 3) If the event occurred at Jefferson, [name] will go into EPIC and verify (and correct if necessary) the information on the Incident Hospitalization/ED Visit Form (for example, incorrect date).
- 4) If the event occurred at a non-Jefferson facility, [name] will fax the release and a request for details about the event to the treating hospital. Once the requested information is received, [name] will verify (and correct if necessary) the information on the Incident Hospitalization/ED Visit Form.
- 5) [name] will enter the verified and corrected data from the Incident Hospitalization/ED Visit Form into REDCap.
- 6) [name] will complete Part 1 of the Event Form and email to [name], [name], [name], and Drs. [name] and [name].
- 7) Drs. [name] and [name] will separately complete Part 2 of the Event Form, and email back to [name], [name], and [name].
- 8) If there is a discrepancy between the responses to Part 2 provided by Drs. [name] and [name], [name] will email the Event Form to [name] to complete. When there is not a majority determination among the 3 physicians, the 3 physicians will be asked to discuss the event and reach consensus.
- 9) [name] will enter each physician's response to Part 2 of the Event Form in REDCap.
- 10) Staff will conduct medical chart reviews for all participants at 6 and 12 months. If when reviewing the charts, staff learns of an ED visit or hospitalization that HAS NOT BEEN PREVIOUSLY reported by staff (i.e., an event for which there is no Incident Hospitalization/ED Visit Form), staff will complete an Event Form, and follow steps 6 through 9. In this situation, an Incident Hospitalization/ED Visit Form will not be completed.

[figure not shown]

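### The physicians who classify events as DM-related are to be masked, but nothing limits their view of a medical record that can reveal the PREVENT arm, and nothing checks their masking

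*Combined protocol and SAP*

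**What the plan says.** All references are to the Manual of Procedures.

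- **Masking rule (8.2).** "Masked staff will not have access to any data files or charts that contain information on treatment assignment". The section lists who is unmasked: the PI, participants, Project Director, Study Coordinator, CHWs, nurse educator and the PCPs of PREVENT participants. Event adjudicators and research assistants are not on that list.
- **Adjudication (6.2).** Of the two co-investigators who decide whether an event is DM-related, the text reads "masked to treatment assignment) will independently review the medical records of all" events. A third physician rates discrepant cases, and discussion settles any that remain.
- **Workflow (Appendix 6).** Staff verify the event, complete Part 1 of an Event Form and email it. The two physicians "will separately complete Part 2 of the Event Form".
- **What enters the record (9.1).** "The CHW will upload the Form to the EMR (Epic) for the PCP's review after sessions 1 and 6". For participants without a Jefferson PCP the form is faxed instead.
- **Back-up assessor (8.2).** A research assistant in the PI's lab "is employed by the Department of Neurology at Jefferson, will be trained to conduct the follow-up assessments". If the Outcome Assessor learns an assignment, "the research assistant will conduct that particular participant's subsequent follow-up assessments".
- **Research Assistant (3.2, 12.4).** This role includes "reviewing participants' medical charts at 6 and 12 months". Section 12.4 describes the person who checks assessment recordings as "The Research Assistant, who is employed by the Department of Neurology at Jefferson and is not paid by this grant".

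**The concern.** The DM-related call defines the primary count. If an adjudicator can tell the arm, the call can drift in one arm and move the rate ratio without any true effect. A masked rating made from a record that differs systematically by arm is protected only if the plan controls what the rater sees. This plan names the masking but gives no means of keeping it and no means of detecting its loss.

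A second, smaller issue concerns the substitution rule for an unmasked Outcome Assessor. It restores masking only if the substitute has not learned the assignment by another route, such as a chart review or the recording on which the disclosure was made.

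**Working it through.** The plan gives no figure on this point, so the check is mainly a side-by-side reading.

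**1. Is the record different by arm?** Yes, for some participants.
- The CHW Encounter Form is a PREVENT form: the treatment process table in 6.2 restricts all forms to PREVENT unless noted, and this one carries no such note. Section 5.6 describes it as used by the PREVENT CHW. No section describes an EUC document being uploaded.
- Appendix 9 files uploads in the chart's Media tab as research documents carrying the study number, with a routing message that names who conducted the visit. It has separate wording for nurse-educator visits, which exist only in PREVENT (9.1, 9.2).
- The PCP telehealth visit runs through MyChart, for Jefferson PCPs only (Appendix 5). EUC has no telehealth (9.2).

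**2. Is the adjudicators' view limited?** Not in the text available. Section 6.2 has them review medical records. Appendix 6 sends them a form but does not say that it replaces the record or what else they may open. No redaction step appears.

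**3. Would unmasking be noticed?** Not for adjudicators. The arm guess and the reporting of unmasking in 8.2 apply to the Outcome Assessor.

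**4. How far does exposure reach?** Only part of the way.
- Three of the four telehealth visits are with the nurse (9.1) and run on Bluejeans (7.12), although Appendix 9 provides for nurse documents to be posted to Epic.
- Forms for non-Jefferson PCPs are faxed, and details of outside events come from the treating hospital.
- Chest pain, UTI and skin infection are all in the Table 3 code list, which anchors those calls.

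**5. Back-up assessor.** Sections 8.2 and 12.4 give the same employer. If this is one person, they review charts at 6 and 12 months (3.2) and listen to each assessment recording within a week (12.4). A disclosure made during a recorded assessment would be on the recording they hear.

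**6. Size, as illustration only.** Let *d* be the share of all events classed DM-related under masked rating, *b* the share that are borderline, *s* the drop in the DM-related call on borderline PREVENT events when the arm is known, and *e* the share of those events where the arm is visible. With EUC calls unchanged, the rate ratio is multiplied by 1 − *e·b·s/d*. None of these inputs is in the documents. Assume *d* = 0.5:

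| *b* | *s* | *e* = 1 | *e* = 0.5 |
|---|---|---|---|
| 0.3 | 0.1 | 1 − 0.03/0.5 = 0.94 | 1 − 0.015/0.5 = 0.97 |
| 0.3 | 0.2 | 1 − 0.06/0.5 = 0.88 | 1 − 0.03/0.5 = 0.94 |
| 0.4 | 0.2 | 1 − 0.08/0.5 = 0.84 | 1 − 0.04/0.5 = 0.92 |

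With *e* = 0 or *s* = 0 the multiplier is 1.00. A drift the other way (*s* negative) would push it above 1. These values show how the mechanism works; they do not estimate its effect.

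**The case against.** The strongest reply has five parts.

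- **The rule in 8.2 may not concern Epic at all.** It stands next to sentences on hard-copy storage and server encryption, and the Manual also uses the word chart for study files (the research chart in 5.5, the two participant charts in 12.3). This stands. A reader might infer a flat contradiction between 8.2 and the adjudication procedure; the text does not establish one. The point rests instead on 6.2, which calls the adjudicators masked and has them review medical records.
- **A staff-prepared Event Form already exists, and no section says adjudicators browse the full chart.** This also stands, so a reader should not infer that they were in fact unmasked. What is shown is access without a stated limit. The content of the Event Form and of section 3.1 was not available here, so a safeguard stated there cannot be excluded.
- **Listed codes, two independent ratings and a third for disagreements limit drift.** They do limit it, but they do not remove it. The dual-rating process presupposes that raters can differ, and both raters could see the same arm-revealing document.
- **The back-up assessor may be someone else.** Section 8.2 speaks of a research assistant without further identification. Identity with the chart reviewer is inferred from the employer, and the role's masking from the purpose of the substitution. The Epic chart check in Appendix 12 lists visits, problem list, history and medications, not the Media tab. That the back-up is already unmasked is therefore not supported, and the point is conditional.
- **Mitigation exists.** The all-cause analysis (13.1.3) needs no DM-related call, and 8.2 has the biostatistician examine bias from unmasking. The first is a useful check. The second has no adjudicator data to work with, because none are collected.

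**Conclusion.** The gap holds in limited form. Adjudicators of the primary outcome are declared masked and work from medical records. For PREVENT participants with a Jefferson PCP those records can reveal the arm, and the plan neither limits what adjudicators see nor checks their masking. This is a correctable weakness in procedure, not evidence that bias occurred.

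The size cannot be derived from the documents. Under the assumptions shown, the multiplier lies between 0.84 and 1.00 if drift favours PREVENT. The low end needs the arm visible for every borderline PREVENT event, which the faxed forms and outside-hospital events make unlikely. Against a hypothesis of halving the event count, even that low end would not by itself produce the hypothesized effect. A reader might take 0.84 to 0.94 as the expected distortion; nothing in the documents supports that.

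The back-up assessor issue applies only if that person is the chart-reviewing Research Assistant.

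**What to change.** **Sections 6.2 and Appendix 6.** State that:
- adjudicators rate only from the Event Form plus the ED or discharge notes and codes for the event dates;
- the Study Coordinator, already unmasked, prepares this packet and removes research documents and telehealth entries;
- adjudicators do not open Epic for this task;
- each adjudicator records a guess of arm for every event;
- the all-cause analysis is reported beside the primary result as a check on classification.

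**Section 8.2.** State whether the back-up assessor is the Research Assistant who reviews charts and recordings. If so, for a substituted participant that person should not listen to the recording in which assignment was disclosed, should complete each assessment before that time point's chart review, and should record their own masking status and arm guess.

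**Do not move chart review or recording checks to unmasked staff.** Chart review detects unreported primary events (6.2), and the recording check allows edits to outcome data in REDCap (12.4). Giving either to people who know the arm would create a new route to bias.

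Recruitment has ended. If events have already been rated, report what the adjudicators saw and consider re-rating from redacted packets.

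**Cost.** Some coordinator time per event and revised wording in the Manual; no new staff.

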8.3. Treatment Fidelity

To monitor treatment fidelity, all treatment sessions (both PREVENT and EUC) will be audio recorded, and Drs. [name] and [name] will review one third of all recordings. The first session, 1 recording randomly selected from sessions 2 through 6, and 1 randomly selected booster session will

be reviewed. Drs. [name] and [name] will listen to the recordings and rate the CHW interventionists' adherence to the treatment protocol using the PREVENT or EUC Treatment Fidelity Rating Form in which the quality of interventionist rapport, delivery of diabetes education, and the delivery of intervention components are rated. Drs. [name] and [name] will discuss their ratings with the respective CHW interventionist for supervisory purposes.

To determine which participants and intervention sessions will be selected for treatment fidelity review, [name] will create a randomization schedule. The schedule will determine: (1) which participants will be selected for treatment fidelity; and (2) which sessions from those participants will be reviewed. The PI will regularly review the interventionists' progress to insure that each he/she is meeting the standard of performance.

